# HD-tDCS as an intervention for cognitive deficits in Alzheimer's dementia: a randomized controlled trial

Sponsor:	Alzheimer's Women's Association for Resources and Education (AWARE), the Dallas Foundation		
Title:	Noninvasive Brain Stimulation in Mild Cognitive Impairment and Dementia		
Trial registration:	ClinicalTrials.gov; NCT05270408		
Document History: Version 0.1	Date March 4, 2024	Author [name]	Modifications Original draft
0.1	March 14, 2024	[name]	Review
0.2	March 14, 2024	[name]	Added sections: design, randomization, sample size calculation, and outcomes. Accepted changes in re- arrangement of analysis details
0.3	March 27, 2024	[name]	Modified analysis methods as follows. Changed effect size calculation from the pooled pretest standard deviation approach (dppc2) to use of Cohen's d . Changed from use of Cochran-Armitage test to Chi-square/Fisher's exact tests in evaluating significance of proportions of clinically meaningful change.
1	July 8, 2024	[name]	Updated. Removed Chi- square/Fisher's exact test from plan.
Version:	Final		
Signature 8/12/2024 Principal Investigator: [name]			

# **Objectives:**

- Determine if HD-tDCS lessens Alzheimer's dementia (AD) associated memory deficits
- Determine if HD-tDCS enhances language, processing speed, and executive functions in AD
- Evaluate if cognitive changes produced from HD-tDCS persist for 8 weeks

# Design:

Participants with a clinical diagnosis of AD or mild cognitive impairment were enrolled. Participants received 10 sessions of 1 mA, 2 mA, or sham HD-tDCS stimulation across 2 weeks. Each HD-tDCS session was 20 minutes in duration and had a 4x1 ring configuration for electrode placement (anode: Fz; cathodes at FPz, Cz, F7, and F8) to deliver stimulation to the dorsal anterior cingulate cortex based on its role in episodic memory functioning and other cognitive skills such as language and executive functions. Cognitive assessments were completed at a baseline visit, immediately following the last HD-tDCS session, and again at a 2-month follow-up visit.

# Randomization:

Participants were randomized at a ratio of 1:2:2 according to the sham, 1 mA, and 2 mA conditions. Randomization of HD-tDCS condition assignments were generated by a computer, and the assignments recorded on cards and placed in sealed envelopes by the PI.

#### **Blinding:**

Participants will be informed that sham and active HD-tDCS will be used in the study, but they will be blinded to condition. Aside from the PI, other study team members who perform assessments will be blinded to HD-tDCS condition, and the subject and study personnel will complete a questionnaire to check if blinding was successful.

# Study sample:

The study sample will be limited to participants with a clinical diagnosis of AD.

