Protocol

HD-tDCS as an intervention for cognitive deficits in Alzheimer's dementia: a randomized controlled trial

Document History: Version 0.1	Date October 21, 2021	Author [name]	Notes Original draft	
1	April 28, 2022	[name]	Modified battery of neuropsychological measures to replace with more comprehensive versions of measures. Included the RAVLT, DKEFS Verbal Fluency, and DKEFS Color-Word Interference test. Corrected written follow-up visit timeline to align with timing of visits expected by study sponsor.	
Version:	Final			
Signature Principal Investigator: [name]				
Sponsor:	Alzheimer's Women's Ass the Dallas Foundation	ociation for Resourc	es and Education (AWARE),	
Title:	Noninvasive Brain Stimulation in Mild Cognitive Impairment and Dementia			
Trial registration:	ClinicalTrials.gov; NCT05270408			
Trial design:	randomized, double-blind, parallel-group sham-controlled trial			
Number of arms:	3			
Trial site:	University of Texas Southwestern Medical Center			
Protocol ID:	STU-2021-0974			
Participant time in trial:	Two months			

Background:

The Alzheimer's Clinical syndrome (ACS) involves the stages of mild cognitive impairment (MCI) and dementia. While recent disease-modifying treatments for Alzheimer's disease show promise to slow cognitive decline, these do not target the cognitive deficits present and are unproven to lessen symptoms. Interventions that can target the damage to memory circuitry in individuals with MCI as well as Alzheimer's dementia (AD) to improve episodic memory is vital to fill an unmet need. Noninvasive neuromodulation therapies have been found to have promising benefits for treating depression and improving cognitive function in patients with and without brain lesions. Specifically, high-definition transcranial direct current stimulation (HD-tDCS) uses an array of small electrodes to pass a low level current through targeted brain regions (e.g., anterior cingulate cortex) to modulate neuronal activity and brain circuitry. HD-tDCS is a safe, portable, and low-cost intervention that offers excellent potential to lessen symptoms in patients with MCI and AD.

Purpose:

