This is a pilot study being done to attempt to improve verbal episodic memory in persons with MCI and AD. Although the hippocampus is a brain structure most often associated with early deficits in MCI and dementia, the dorsal anterior cingulate cortex (DACC) has been shown to play a role in verbal episodic memory for such patients. Delivery of HD-tDCS to the DACC may have potential to entrain the circuit involved in episodic memory, and as such, may improve the functioning of the circuit and lessen symptoms. The purpose of the pilot study is to examine the efficacy of HD-tDCS to the DACC region and its influence on verbal episodic memory in patients with MCI and dementia.

Primary Objective:

• Determine if HD-tDCS lessens memory deficits associated with ACS

Secondary Objective:

- Determine if HD-tDCS enhances language, processing speed, and executive functions in ACS
- Evaluate if cognitive changes produced from HD-tDCS persist for 8 weeks

Design:

Participants with a clinical diagnosis of AD as well as MCI will be enrolled. Participants will receive 10 sessions of 1 mA, 2 mA, or sham HD-tDCS stimulation across 2 weeks. Each HD-tDCS session will be 20 minutes in duration and have a 4x1 ring configuration for electrode placement (anode: Fz; cathodes at FPz, Cz, F7, and F8) to deliver stimulation to the DACC. Cognitive assessments will be completed at a baseline visit, immediately following the last HD-tDCS session, and again at a 2-month follow-up visit.

Patients randomized to recieve: 0 mA, 1 mA, or 2 mA condition 10 days of HD-tDCS

Cognitive tests after the 10th session

Cognitive tests

Cognitive tests

SUMMARY OF VISITS			
Visit	PROCEDURES	TIME	
Visit 1	Pre-testing neuropsychological assessment	1 hour	
Visits 2-10	HD-tDCS active or sham stimulation	30 minutes	
Visit 11	HD-tDCS active or sham stimulation and post-testing neuropsychological assessment	1 hour 30 minutes	
Visit 12	8-week follow-up assessments	1 hour	

Inclusion criteria:

- 1. Age 50 and older
- 2. Fluent in English
- 3. Active diagnosis of MCI or Alzheimer's dementia

Exclusion criteria:

- 1. Substance use disorder within past year
- 2. Has metal fragments or implants in head
- 3. Traumatic brain injury within past year
- 4. Lifetime major medical that could be a contraindication to safety (e.g., epilepsy)

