DKEFS Color-Word Interference. This test measures processing speed in the control conditions of word reading and color naming, measures executive functions of inhibitory control in the interference condition, and cognitive flexibility in the switching condition. The interference condition is where the

color word names are written in a different ink color than the name. The switching condition is where the patient must switch back-and-forth between the response patters of naming the ink color and reading the word. The outcome measure for this task is the time to complete each of the four conditions.

Southwestern Assessment of Processing Speed (SWAPS). This is an assessment of processing speed. The patient is required to transcribe numbers to their corresponding written symbol as quickly as possible within 60 seconds. The outcome measure for this task is the total number of correct responses.

Subject safety monitoring: All HD-tDCS sessions will be overseen by the PI. All safety precautions recommended by scientific literature and the UT Southwestern IRB will be carefully followed. All adverse events volunteered by the subject or elicited by the research team will be recorded in the subjects' research file. All adverse events will be reported within one week to the IRB. Any severe adverse events will be reported within 24-48 hours to the IRB.

In order to safeguard our participants from a breach in confidentiality, the data is coded with a unique semi-random subject identifier (URSI). All data after initial entry into the study is coded based on the participant's number. A digital file containing completed questionnaires and assessments from the experimental session will be maintained with the URSI number. These files will be kept in an encrypted, IRB approved database (RedCap).

Statistical analysis: General linear models will be used to evaluate whether outcomes significantly change as a function of treatment allocation (sham, 1 mA HD-tDCS, 2 mA HD-tDCS). Changes from baseline on the outcomes of interest will be assessed. Participants with missing time points will not be excluded. All available data on all participants who 1) meet inclusion/exclusion criteria, 2) have been randomly assigned to groups, and 3) provide baseline data will be included regardless of whether they complete the trial.

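### The SAP analyses only AD participants, although the protocol's primary objective and analysis set cover all eligible randomised MCI and AD participants

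*SAP*

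**What the plan says.** **Protocol.** Inclusion criterion 3 is "Active diagnosis of MCI or Alzheimer's dementia". The primary objective is "Determine if HD-tDCS lessens memory deficits associated with ACS", and the Background says that ACS "involves the stages of mild cognitive impairment (MCI) and dementia". The Statistical analysis paragraph includes "All available data on all participants who 1) meet inclusion/exclusion criteria, 2) have been randomly assigned to groups, and 3) provide baseline data", whether or not they complete the trial. Diagnosis does not limit that set.

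**SAP.** The Design section agrees on enrolment: "Participants with a clinical diagnosis of AD or mild cognitive impairment were enrolled". The Study sample section then states: "The study sample will be limited to participants with a clinical diagnosis of AD". The first two objectives are worded for AD alone; the second, for example, reads "Determine if HD-tDCS enhances language, processing speed, and executive functions in AD". Analysis Methods, Missing data and Multiple comparison correction contain no analysis of the combined set, no MCI analysis and no sensitivity analysis on population. The Document History records changes to the effect size and the tests, but none to the population. The statement about changes in the Outcomes section concerns outcomes only.

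**The concern.** Two different populations are specified for the same primary analysis, and nothing reconciles them. Three things are at stake.

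- **The question answered.** The protocol asks about ACS. An AD-only analysis answers a narrower question, and the plan does not say where the MCI results will be reported.
- **Precision and balance.** The trial has no power calculation and allocates one fifth of participants to sham. Neither document describes stratification by diagnosis, so the 1:2:2 split is not protected within AD. That affects precision and balance; it is not in itself bias.
- **Credibility.** The SAP was first drafted in March 2024, reached version 1 in July 2024 and carries a signature date of 8/12/2024. The protocol's version 1 dates from April 2022. The PI signs the SAP and, under the protocol's Procedures, knows how the conditions were labelled. A reader cannot tell whether the population was chosen without knowledge of results.

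**Working it through.** **Step 1: who is in one set and out of the other.** Take a participant with MCI who meets the criteria, was randomised and has baseline data.

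| Source | Included? |
|---|---|
| Protocol, Inclusion criteria | Yes, MCI qualifies |
| Protocol, Primary Objective with Background | Yes, MCI is a stage of ACS |
| Protocol, Statistical analysis | Yes, all three conditions are met |
| SAP, Design | Yes, as enrolled |
| SAP, Study sample | No |

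AD cannot be read as covering MCI, because the SAP Design section lists the two as alternatives. The conflict is therefore real and does not depend on any number.

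**Step 2: what the documents show about timing.** The version 0.2 log entry reads "Added sections: design, randomization, sample size calculation, and outcomes". The Design and Randomization text is in the past tense, which fits a SAP written after enrolment. This is weak evidence, since tense is mixed in both documents. Neither Study sample nor Objectives is in that list, so the restriction may have been in the original draft of March 4, 2024. The date of the decision and access to outcome data by arm are not stated.

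**Step 3: loss of precision (illustration).** The documents give no N and no MCI share, so there is no plan figure to reproduce. Assumptions: MCI share m; ratio r of MCI to AD residual variance; equal arm proportions within each diagnosis; a common treatment effect.

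- Full-set variance is proportional to [(1−m) + m·r]/N.
- AD-only variance is proportional to 1/[N(1−m)].
- Standard-error inflation = 1/√{(1−m)·[(1−m) + m·r]} − 1.

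Examples at m = 0.5: with r = 1, 1/√(0.5 × 1) − 1 = 41.4%; with r = 2, 1/√(0.5 × 1.5) − 1 = 15.5%.

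| MCI share dropped | r = 1 | r = 1.5 | r = 2 |
|---|---|---|---|
| 10% | 5.4% | 2.9% | 0.5% |
| 20% | 11.8% | 6.6% | 2.1% |
| 40% | 29.1% | 17.9% | 9.1% |
| 50% | 41.4% | 26.5% | 15.5% |
| 60% | 58.1% | 38.7% | 25.0% |

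**Step 4: size of the sham AD group (illustration).** Assume half the participants have AD. The expected number of sham AD patients is N × 1/2 × 1/5 = N/10. The documents do not say whether allocation was simple or held to exact 1:2:2 totals, so both are shown.

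| Assumed N | Expected sham AD | P(≤2), exact totals: hypergeometric (N, N/5, N/2) | P(≤2), simple: binomial (N/2, 0.2) |
|---|---|---|---|
| 30 | 3 | 32.6% | 39.8% |
| 40 | 4 | 11.8% | 20.6% |
| 50 | 5 | 3.7% | 9.8% |

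**The case against.** The strongest defence is that an AD focus is visible from the start: both documents are headed with a title naming Alzheimer's dementia, so the SAP might be the plan for the AD report of a wider project. The documents never say so, and both also carry a second title naming MCI and dementia. A title neither overrides the objective and analysis set nor supplies a reason.

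Other points stand in part:

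- **Log.** If the restriction was in the first SAP draft, no later SAP log entry would be due. True, so the missing entry does not show a late change. The departure from the protocol remains unexplained.
- **Tense and PI knowledge.** Neither shows that the choice was driven by data. Agreed; the point is only that independence from the results is undocumented.
- **Valid comparison.** The natural reading is that AD means the diagnosis at entry. On that reading AD-only is still a randomised comparison. The SAP should say so, but no bias is shown.
- **Hypothetical magnitude.** The range runs from 0.5% to 58% and assumes a common effect. If effects differ between MCI and AD, the two sets answer different questions and comparing standard errors does not decide between them. The figures are therefore illustrations and do not carry the conclusion.
- **Covariate.** Adjusting for diagnosis appears in neither document. It is a recommendation beyond restoring the protocol's set.

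None of this removes the conflict or provides the missing full-set analysis.

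**Conclusion.** The concern holds, and the plan must be changed. As written, the SAP excludes eligible randomised MCI participants whom the protocol's analysis set includes, and it leaves the ACS objective without an analysis. That conclusion rests on the text alone.

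The statistical cost depends on facts not stated. It is slight if few MCI participants were enrolled and substantial if they were about half: 15% to 41% wider standard errors for r between 2 and 1. At an assumed N of 40 with half AD, there would be a 12% to 21% chance of two or fewer sham AD patients. No bias and no selection on results is demonstrated.

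**What to change.** **Preferred.** Make the protocol's set (all randomised eligible MCI and AD participants with baseline data) the primary analysis population. Add entry diagnosis as a covariate next to the baseline score. Report AD-only as a labelled subgroup, and treat any arm-by-diagnosis estimate as descriptive only.

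**If AD-only stays the headline:**

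- report the full-set result beside it;
- state the date and reason for the restriction, and whether those deciding it had seen outcome data by arm;
- define AD by the diagnosis recorded before allocation;
- limit the conclusion to AD.

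**Cost.** SAP wording, one log entry and one extra covariate; no new data. The downside is a headline estimate that averages over a more mixed population, which the covariate and the AD-only result partly address.

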#### Sample size calculation:

No power analysis was performed for the study.

# **Outcomes:**

## Primary

Episodic memory functioning will be assessed through standardized scores in Total Learning and Delayed Recall for the RAVLT (verbal memory).

# Secondary

- Visual memory will be assessed through standardized scores in Total Learning and Delayed Recall for the BVMT-R.
- Language will be assessed through standardized scores for the Boston Naming Test, DKEFS Phonemic Fluency, and DKEFS Category Fluency.
- Processing speed will be assessed through standardized scores for the SWAPS, TMT A, DKEFS Color Naming, and DKEFS Word Reading.
- Executive functions will be assessed through standardized scores for TMT B, DKEFS Category Fluency Switching, DKEFS Inhibition, DKEFS Inhibition/Switching.

Changes to outcomes: There were no changes to outcomes after the trial commenced.

# Analysis Methods:

Two pairwise comparisons will be used to evaluate whether cognitive performance following the last treatment session statistically differs between HD-tDCS conditions, covarying for pre-treatment scores. This will consist of sham versus 1 mA and then sham versus 2 mA conditions. Eta effect sizes produced from the two comparisons will be transformed to Cohen's d and examined.

Clinically meaningful change associated with HD-tDCS will also be assessed. Proportions of individuals with a 5+ standardized score increase (T-score) on each measure of cognitive functioning will be characterized and evaluated. This will be completed examining sham versus 1 mA and then sham versus 2 mA conditions.

For the exploratory objective, those outcome measures identified to show significant changes immediately following the last treatment session (via statistical or Cohen's  $d \ge .50$ ) will be evaluated for this aim. Pairwise comparisons will be used to evaluate if scores at the 8-week follow-up statistically differ between HD-tDCS conditions (sham versus 1 mA; sham versus 2 mA), while covarying for the pre-treatment scores. Eta effect sizes produced from comparisons will be transformed to Cohen's d and examined.

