#### Missing data:

In the event few scores of executive function are available (due to tests being discontinued from cognitive impairment), alternative indices will be derived and examined post-hoc. Number of items not completed when the time limit is reached will be summed (higher scores representing lower performance) for TMT B, DKEFS Inhibition, and DKEFS Inhibition/Switching measures. Scores will be examined in ANCOVA models and effect sizes, but not as indices for clinically meaningful change.

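### Cohen's d is derived from Eta-squared with no sign rule and no stated type, so the d ≥ .50 gate for the 8-week analysis can admit measures on which sham did better and has no fixed meaning

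*SAP*

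**What the plan says.** SAP, Analysis Methods: the post-treatment analysis asks whether performance "statistically differs between HD-tDCS conditions, covarying for pre-treatment scores". On the comparisons: "This will consist of sham versus 1 mA and then sham versus 2 mA conditions". Eta-squared "effect sizes produced from the two comparisons will be transformed to" Cohen's d. The 8-week analysis is then limited to "those outcome measures identified to show significant changes immediately following the last treatment session", where a measure qualifies by statistical significance or by d ≥ .50. The same Eta-squared conversion is repeated at 8 weeks.

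SAP, Missing data, adds replacement executive-function indices on which a higher score is worse: "Scores will be examined in ANCOVA models and effect sizes". SAP, Randomization: "Participants were randomized at a ratio of 1:2:2 according to the sham, 1 mA, and 2 mA conditions".

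The SAP does not give the conversion formula, the type of Eta-squared (classical or partial), the SD that d is meant to be expressed in, or a rule for assigning a sign to d. It does not say which direction a significant difference must have to qualify.

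**The concern.** Eta-squared is a share of variance. It records how large a difference is, not which arm was better. A d computed from it alone is an absolute value, and a threshold of .50 on an absolute value treats harm and benefit alike. The replacement indices make this worse, because their raw direction is the reverse of the other scores.

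The scale is also open. Partial Eta-squared removes the variance explained by the baseline score from the denominator, so the resulting d is in residual-SD units. Classical Eta-squared keeps that variance. Two analysts following the SAP on the same data could report different d values and fall on opposite sides of .50.

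At stake are the d values reported at both time points and the list of measures tested for persistence. The SAP calls the 8-week aim exploratory in its methods, but the protocol lists persistence at 8 weeks among its secondary objectives.

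**Working it through.** **Inputs from the SAP.** Baseline-adjusted comparisons, sham versus each active arm; allocation 1:2 in each; gate d ≥ .50 or p < 0.05; 15 measures (2 primary; 2 + 3 + 4 + 4 secondary), so 30 comparisons.

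**Assumptions, because the documents give no figures.** Sham/active sizes of 5/10, 10/20 and 20/40; pre-post correlation r from .5 to .9; separate two-arm ANCOVAs; conversion d = 2·√f², with f² = η²/(1 − η²). The plan contains no computed d to reproduce. Under this conversion, d = .50 means f² = 0.0625 and η² = 0.0625/1.0625 = 0.0588.

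**Step 1, sign.** The group sum of squares is proportional to the square of the adjusted difference, so η² is the same for +δ and −δ. With no true effect the adjusted difference is symmetric about zero, so half of the passing measures favour sham. With sham truly better by 0.50 SD, r = .7 and 10/20, simulation passes the gate in about 69% of trials with partial Eta-squared and about 47% with classical. A signed d passes in 0%.

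**Step 2, scale.** Take within-arm score variance as 1, groups large and 1:2, so that the product of the group shares is (1/3)(2/3) = 2/9.
- Classical: f² = d²·(2/9), so reported d = 2·√(2/9)·d = 0.943·d. A true 0.50 is reported as 0.47.
- Partial: f² = d²·(2/9)/(1 − r²), so reported d = 0.943·d/√(1 − r²).

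| r | inflation 1/√(1 − r²) | reported d for a true 0.50, partial | true score-SD d at a reported .50, partial |
|---|---|---|---|
| .5 | 1.15 | 0.54 | 0.46 |
| .7 | 1.40 | 0.66 | 0.38 |
| .8 | 1.67 | 0.79 | 0.32 |
| .9 | 2.29 | 1.08 | 0.23 |

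**Step 3, how often the gate opens with no effect.** For partial Eta-squared, F = f²·df, so the gate is F ≥ 0.0625·df on 1 and df degrees of freedom, with df = n0 + n1 − 3.
- 5/10: df = 12, F ≥ 0.75, 40% (about 12 of 30 comparisons)
- 10/20: df = 27, F ≥ 1.69, 20% (about 6 of 30)
- 20/40: df = 57, F ≥ 3.56, 6% (about 2 of 30)

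For classical Eta-squared at 5/10, simulation gives about 30%, 22%, 15% and 6% at r = .5, .7, .8 and .9.

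**Step 4, group sizes.** A conversion that uses the actual sizes replaces the factor 2 by √(df·(1/n0 + 1/n1)). This is √(12 × 0.30) = 1.897 at 5/10, √(27 × 0.15) = 2.012 at 10/20, and tends to √4.5 = 2.121. In two-arm models at these sizes the equal-size formula is therefore off by about 6% at most, and at 5/10 it errs upward.

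**The case against.** The strongest reply is that this is a step left unspecified, not an error. Direction can be read from the adjusted means of the same model, and d ≥ .50 can be read as a signed threshold. The SAP writes Eta-squared without the word partial, and the classical form returns nearly the right scale. Following an adverse change to 8 weeks may even be intended, since the objective speaks of cognitive changes persisting.

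Much of this stands. A reader might infer that the d values and the gate are wrong; the documents show only that they are unsigned and under-defined. A reader might infer that every d is inflated; that holds only for partial Eta-squared. On the classical reading, changing the metric does not reduce chance passes: at 5/10 with no effect, the absolute value of the proposed d reaches .50 in about 32%, 24%, 17% and 7% of comparisons for r of .5, .7, .8 and .9, slightly more often than classical. There the gain comes from the sign alone.

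A reader might also infer that the conversion ignores the 1:2 allocation. The SAP gives no formula, so this cannot be shown, and in two-arm models the effect is minor. It would be larger (about 20 to 27% understatement) only for contrasts within one three-arm model, which the SAP neither states nor excludes.

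The reply does not supply the sign rule or the type of Eta-squared. That a careful analyst could restore them does not make them pre-specified.

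**Conclusion.** The point holds as a gap in specification with a real consequence. Followed literally, the SAP produces an unsigned d and a gate that can select measures on which sham did better; this does not depend on which Eta-squared is used. The .50 threshold has no fixed meaning because the type of Eta-squared is open: under the partial form it corresponds to a true score-SD difference of 0.46 down to 0.23 for r of .5 to .9. The pass rates and inflation figures rest on assumed group sizes and correlations and on the equal-size conversion.

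The reach is limited. Post-treatment p-values and the proportions with a 5-point gain are untouched. What is affected is the reported d and the choice of measures tested at 8 weeks. With no power analysis and no multiplicity adjustment, those d values are likely to carry weight in interpretation, so the text should be settled before results are reported.

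**What to change.** Replace the Eta-squared conversion at both time points.

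1. Report the baseline-adjusted mean difference, active minus sham, with its 95% CI.
2. Compute d as that difference divided by one named SD, for example the pooled baseline SD of the analysed sample. Apply a small-sample correction and give a 95% CI.
3. Sign d so that positive favours active, reversing the replacement indices on which higher is worse.
4. Apply the .50 threshold to this signed d, and state the direction required for the p < 0.05 route. If adverse changes are also to be followed to 8 weeks, say so and report them separately.

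Cost: SAP wording and a few lines of code, with no new data. If results already exist, d can be recomputed from the same fitted models, with the change dated and disclosed. The downside is that d will be smaller than values derived from partial Eta-squared, and fewer measures will pass the gate.

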Screening and consenting strategy: Prospective participants will undergo telephone screening for conditions in their medical history as well as current medications. Prospective participants meeting pre-screening inclusion/exclusion criteria will be scheduled an appointment to review the study procedures and Consent Form. Study staff will go over the consent form in detail with the prospective participant and answer any questions about the procedures. Participants or the legal authorized representative will be asked to sign the Consent Form if they understand the study procedures, appreciate potential risks/benefits, and desire to be involved in the study.

Timing and procedures of follow-up: Cognitive evaluations will be completed immediately after session 10 and 2-months later. Patients will be called back for the 2-month follow-up.

Outcomes:

Primary

Episodic memory functioning will be assessed through standardized scores in Total Learning and Delayed Recall for the Rey Auditory Verbal Learning Test (verbal memory).

Secondary

- Visual memory will be assessed through standardized scores in Total Learning and Delayed Recall for the BVMT-R.
- Language will be assessed through standardized scores for the Boston Naming Test, DKEFS Phonemic Fluency, and DKEFS Category Fluency.
- Processing speed will be assessed through standardized scores for the SWAPS, TMT A, DKEFS Color Naming, and DKEFS Word Reading.
- Executive functions will be assessed through standardized scores for TMT B, DKEFS Category Fluency Switching, DKEFS Inhibition, DKEFS Inhibition/Switching.

Rey Auditory Verbal Learning Test (RAVLT). A 15-item list learning and memory task where the tester reads aloud a list of nouns. The RAVLT includes 5 learning trials, an interference trial, a delayed recall trial, and a yes/no delayed recognition trial. The tester records how many items the patient remembers over several repeated trials and then again for the interference and 30-minute delayed recall trial. The RAVLT is a direct measure of verbal episodic memory and has multiple alternate forms. The scores forTotal Learning and Delayed Recall are the outcomes of interest.

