#### Multiple comparison correction:

Statistical significance will be set at p < 0.05 with no correction for multiple comparisons to reduce the chances of a Type II error given the small sample size of the pilot study.

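### The SAP compares arms at 8 weeks only for measures that pass a post-treatment screen; the two primary RAVLT scores are not exempt, so either or both can end with no 8-week comparison

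*SAP*

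**What the plan says.** The Objectives section of the SAP includes "Evaluate if cognitive changes produced from HD-tDCS persist for 8 weeks", and the protocol lists the same aim under Secondary Objective. Neither list restricts it to particular measures. The 8-week assessment does not depend on the earlier result: the protocol (Timing and procedures of follow-up) says "Patients will be called back for the 2-month follow-up", and the SAP (Design) reports that "Cognitive assessments were completed at a baseline visit, immediately following the last HD-tDCS session, and again at a 2-month follow-up visit".

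The SAP's only 8-week analysis is in the last paragraph of Analysis Methods. It takes forward "those outcome measures identified to show significant changes immediately following the last treatment session", judged by the statistical test or by d of at least .50. For those measures, "Pairwise comparisons will be used to evaluate if scores at the 8-week follow-up statistically differ between HD-tDCS conditions", as sham versus 1 mA and sham versus 2 mA, adjusted for baseline. The responder paragraph before it names no 8-week time point.

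The primary outcome is the pair of RAVLT scores, Total Learning and Delayed Recall (SAP Outcomes, Primary). No section exempts them from the screen. The protocol's Statistical analysis section plans models of change from baseline on the outcomes of interest with no such screen, but it names no 8-week contrast and so does not fill the gap.

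**The concern.** The screen works measure by measure. If one RAVLT score misses both thresholds after the last session, the SAP gives it no 8-week comparison; if both miss, the primary outcome has none. Persistence is a stated objective and the data are collected, so the gap would come from the analysis rule alone.

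Two things are at stake. The first is a missing estimate on the primary measures. In small arms, failing the screen is weak evidence that nothing changed. The second is selection. Measures reach the 8-week table because their post-treatment estimate was large, partly by chance. Post-treatment and 8-week scores are correlated, so the reported 8-week effects inherit some of that excess.

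**Working it through.** The gap itself follows from the text. Its size needs assumptions, because the SAP (Sample size calculation) reports no power analysis and neither document gives arm sizes. There is no planned figure to reproduce.

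**Inputs from the SAP.** Allocation: "Participants were randomized at a ratio of 1:2:2 according to the sham, 1 mA, and 2 mA conditions". Threshold: "Statistical significance will be set at p < 0.05 with no correction for multiple comparisons" (taken as two-sided). Alternative route: d of at least .50, converted from Eta-squared.

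**Assumptions.**
- Analysed sham n (n0) of 5, 8, 10, 15 or 20.
- Correlations: pre–post .7, post–follow-up .7, pre–follow-up .6, between RAVLT scores .7.
- The same true benefit of 0.3 SD in both active arms, on both scores, at both times.
- A score passes if either contrast passes, and both contrasts are then tested at 8 weeks.
- d is taken without sign.

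**Step 1: the screen.** Each contrast is a baseline-adjusted model on two arms, with df = n0 + 2·n0 − 3 = 3·n0 − 3. The SAP gives no conversion formula, so I use d = 2√(η²/(1 − η²)). It does not say whether Eta-squared is partial, t²/(t² + df), or classical, SS(arm)/SS(total), so both are shown. With the partial form d = 2|t|/√df, so d ≥ .50 means |t| ≥ 0.25√df:
- n0 = 5: df = 12, |t| ≥ 0.87, p ≤ 0.40
- n0 = 10: df = 27, |t| ≥ 1.30, p ≤ 0.20
- n0 = 20: df = 57, |t| ≥ 1.89, p ≤ 0.064

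At these sizes the d route is the easier one.

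**Step 2: chance of no 8-week comparison at a true 0.3 SD** (simulation; repeat runs agree to about 0.01).

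| Sham n | 5 | 8 | 10 | 15 | 20 |
|---|---|---|---|---|---|
| At least one RAVLT score out, partial | 0.47 | 0.55 | 0.58 | 0.62 | 0.64 |
| At least one out, classical | 0.68 | 0.76 | 0.78 | 0.76 | 0.69 |
| Both out, partial | 0.16 | 0.25 | 0.29 | 0.34 | 0.37 |
| Both out, classical | 0.36 | 0.48 | 0.53 | 0.51 | 0.42 |
| Both out if p < 0.05 were the only route | 0.74 | 0.67 | 0.62 | 0.51 | 0.42 |

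**Step 3: sensitivity.**
- Varying the correlations (between scores .5 or .9; pre–post .5 or .8): at least one out 0.41–0.74 (partial) or 0.56–0.82 (classical).
- True benefit of 0.5 SD: at least one out 0.22–0.30 or 0.26–0.51; both out 0.08–0.10 or 0.09–0.25.
- Reading 0.3 in residual-SD units, a smaller effect of 0.3 × √(1 − 0.7²) = 0.21 SD, with between-score correlation .8: both out 0.21, 0.42 and 0.59 at sham n 5, 10 and 20 (partial).

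**Step 4: selection.** Among scores that pass, the mean 8-week estimate is about 0.36–0.38 SD (partial) or 0.38–0.44 SD (classical), against a true 0.30.

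**Step 5: significant findings forgone.** The chance of p < 0.05 at 8 weeks per contrast, without and with the screen (partial), is 0.094 and 0.081 at sham n 5, 0.124 and 0.102 at 8, and 0.152 and 0.122 at 10. That is a loss of about 1 to 3 percentage points; under the classical form it is about 3 to 6. At sham n 20 it is 0.27 against 0.19 (partial).

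**Step 6: under the null.** Counting every planned contrast, the screen yields p < 0.05 at 8 weeks in 0.04, 0.03 and 0.03 of cases at sham n 5, 8 and 10 (partial). Among scores that pass, the rates are 0.06, 0.07 and 0.08.

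**The case against.** The best defence is that the screen follows from the question. Persistence presupposes a change, so testing only measures that changed is a natural, pre-specified reading in a declared pilot. That is a good reason to look first at measures that changed. It is not a reason to give no estimate for the others, least of all the primary ones, when an arm may be too small to show a change that occurred.

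It is also fair that little is lost in significant findings: 1 to 3 points per contrast in small arms under the partial form. An unscreened estimate would be imprecise. With residual SD √(1 − 0.6²) = 0.8, its standard error is about 0.8 × √(1.5/n0), or 0.44, 0.35 and 0.31 SD at sham n 5, 8 and 10 (about 0.46 at n 5 once estimation of the baseline slope is allowed for). Under the partial form the selection excess of 0.06–0.08 SD is roughly an eighth to a quarter of that (0.06/0.46 = 0.13; 0.08/0.31 = 0.26). These points stand and limit the severity.

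Three stronger readings are tempting but unsupported:
- *The screen inflates 8-week false positives.* Over all planned contrasts it lowers them (Step 6). Only the rate among scores that pass is above 0.05.
- *The lenient d threshold causes the loss.* It is an alternative to p < 0.05, so it can only add measures; Step 2 shows that the p-value alone would drop more.
- *The primary analysis is compromised.* The post-treatment RAVLT comparison comes before the screen and is unaffected.

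**Conclusion.** The SAP's rule can leave one or both primary scores with no 8-week comparison, although persistence is an objective in both documents and the visit is held regardless. The effects it does report at 8 weeks are too large on average. Under the assumptions above, with a true sustained 0.3 SD, at least one RAVLT score is lost about half to three-quarters of the time and both about one-sixth to one-half of the time. Those figures move with the arm size and effect scale, which the documents do not give; the textual gap does not.

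The main cost is missing and selected estimates rather than lost significance or extra false positives. Severity is minor to moderate. The use of the word exploratory for an aim that neither objectives list labels so, the unstated type of Eta-squared, and the lack of a direction rule for d are minor wording matters. A direction rule would not cure the gap: counting only passes that favour active stimulation, both scores are out with probability 0.27–0.37 (partial).

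**What to change.** In the SAP's Analysis Methods, exempt both RAVLT scores from the screen. Report their baseline-adjusted 8-week comparisons, sham versus 1 mA and sham versus 2 mA, as signed differences with 95% CIs whatever the post-treatment result. Keep the planned 8-week tests for other measures that pass, and give estimates with CIs, labelled descriptive, for those that do not. State the type of Eta-squared and attach a sign to d. The SAP already describes the assessments in the past tense; if results are known, label the added analyses post hoc.

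The cost is some wording, a few model runs, a longer table and wide intervals. Under the null, expected chance RAVLT results at 8 weeks rise to 2 scores × 2 contrasts × 0.05 = 0.20. With the screen, at sham n 5 to 10, they are about 0.11–0.15 (partial; 4 × 0.037 = 0.15 at n 5) or 0.06–0.10 (classical; 4 × 0.026 = 0.10 at n 5 and 4 × 0.014 = 0.06 at n 10). With all 15 scores shown, 15 × 2 × 0.05 = 1.5 of the 30 intervals would exclude zero by chance, so the descriptive label needs to be plain.
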